**•Specific Aim 3**

For this Aim the primary endpoint is the change in 24 hr cortisol concentration from baseline in response to CPAP treatment. There are two time points of interest: baseline (T1) and end of study after receiving six weeks of CPAP (T2). If the variance in cortisol is denoted by  $\sigma^2$  and the correlation between pre- and post-treatment cortisol by  $r$ , then the variance of the change in cortisol is given by  $2\sigma^2(1-r)$ . With 20 subjects and assuming a two-sided alpha level of 0.05, the **Table D3-2** below lists the cortisol change detectable with 80% power for varying values of  $r$ .

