**Specific Aim 2. To determine if OSA improves in women with PCOS treated with estrogen or progesterone.** For these studies, we will enroll women with PCOS who have OSA. Subjects will have a detailed baseline metabolic and metabolomic profile together with a baseline polysomnogram. Subjects will then receive a single dose of depot-leuprolide in order to suppress ovarian production of estrogen, progestin, and androgen over a period of 3 months. Six weeks after administration of depot-leuprolide, subjects will have repeated assessment of metabolic, metabolomic, and sleep measures to determine if these outcomes are altered by the combined suppression of ovarian sex steroids. Subsequently, subjects will be randomized in a double-blind placebo controlled fashion to one of two treatment arms for a period of six weeks. Treatment arms are: estrogen plus placebo or progesterone plus placebo. At the end of this second six weeks, subjects will have metabolic, metabolomic, and sleep measures repeated. Primary outcome measures will be compared both within and between treatment arms.

**Specific Aim 3. To determine if metabolic disturbances present in PCOS women with OSA are ameliorated by the treatment of OSA with continuous positive airway pressure (CPAP).** The presence of OSA in women with PCOS has a significant negative effect upon metabolic measures. In particular, the presence of OSA in PCOS is associated with hyperinsulinemia, elevations in plasma glucose, and lipid abnormalities that include higher levels of triglycerides and LDL-cholesterol. OSA in PCOS is also associated with hypercortisolemia that persists throughout both day and night. Results of our preliminary studies indicate that CPAP treatment of OSA results in attenuation of cortisol levels not only during sleep, but throughout waking hours as well. This aim will serve to test the hypothesis that correction of OSA in PCOS will lead to improved metabolic function which can be attributed, at least in part, to a reduction in circulating levels of cortisol.

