**Figure D1-1. Schematic of overall study design for Specific Aims 1 - 3.**

hyperplasia, Cushing syndrome, hypothyroidism, or significant elevations in serum prolactin. Thus, all subjects will meet the so-called NIH criteria for PCOS (113) as well as the Rotterdam criteria for PCOS (114). For at least 2 months before the study, all subjects must not take steroid preparations (including oral contraceptives), medications known to alter insulin secretion and/or action, or medications known to influence sleep. All studies will be conducted in the follicular phase of the menstrual cycle (days 1 – 7) or after 2 or months of amenorrhea. A negative pregnancy test will be required prior to all testing procedures. Subjects who are known to be diabetic will be excluded; those who prove to be diabetic on screening will not continue in subsequent protocols. Subjects with hypertension (systolic > 140 mmHg and/or diastolic > 90 mmHg) will be included only if well-controlled on stable medication with either ACE inhibitors or diuretics. Subjects on beta-blockers will be excluded as these drugs affect both insulin sensitivity and sleep. Subjects must have regular life styles (no shift work, no travel across time zones within 4 weeks of study), and habitual bedtimes. Other exclusion criteria will be: habitual alcohol use of more than 2 drinks per day and excessive caffeine intake of more than 300 mg per day.

Table D1. Summary Grid of Tests by Specific Aim.	SPECIFIC AIM 1		SPECIFIC AIM 2		SPECIFIC AIM 3
	Obese PCOS OSA Negative	Obese PCOS OSA Positive	Obese PCOS OSA Positive		Obese PCOS OSA Positive
			Depot Leuprolide	Depot Leuprolide	
			Estrogen plus Placebo	Progesterone plus Placebo	CPAP
SAMPLE SIZE	23	23	20	20	20
Oral glucose tolerance test (OGTT)	2	2	2	2	2
Frequently sampled IVGTT (fsIVGTT)	2	2	2	2	1
Androgen levels (total, free T, et al.)	1	1	2	2	2
Estradiol, Estrone, Progesterone	1	1	2	2	2
Gonadotropins (LH, FSH)	2	2	2	2	2
Metabolomics profile (blood, urine)	2	2	2	2	2
24 hr hormonal profiles (including Cortisol and Catecholamines)	2	2	2	2	1
Plasma catecholamines	2	2	2	2	2
Abdominal MRI, Bioimpedance	2	2	2	2	2
Adipose tissue biopsy	2	2	2	2	2
Serum for adiponectin	2	2	2	2	2
Sleep and Activity Assessment	2	2	2	2	2
Sleep questionnaires	2	2	2	2	2
Wrist activity monitoring	2	2	2	2	2
Multiple sleep latency test (MSLT)	2	2	2	2	2
Sleep recording/Polysomnography	1	1	1	1	1
Wake EEG/Neurobehav. assessments	2	2	2	2	2

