After this midpoint assessment, subjects will again enter into a randomized phase of the protocol. Subjects will be assigned to receive one of two treatment regimens in a randomized, double-blind, placebo controlled fashion, for a period of 6 weeks. Subjects will receive daily oral doses of either **2 mg micronized estradiol (Estrace®) plus placebo –OR– 200 mg micronized progesterone (Prometrium®) plus placebo.**

Rationale for preparation and dose of estrogen and progesterone. Natural estradiol is poorly absorbed in its native form and undergoes rapid metabolism in a first-pass effect through the liver. Thus, micronization (micronized estradiol) or acetylation (ethinyl estradiol) is required to achieve adequate blood hormone levels. Micronized estradiol is extremely well-absorbed and much of the compound is metabolized to estrone sulfate (65%) and estrone (15%). This “pool” of estrone and estrone sulfate then serves as the source of regenerated estradiol. At a dose of 2 mg per day, the steady-state levels of estradiol and estrone are typically 220 pmol/L and 68 pmol/L, respectively (116) and most closely recapitulate those seen in normal women in the midfollicular phase of the menstrual cycle (110). Because ethinyl estradiol is poorly converted to estrone, it will not be selected for use in these protocols. Micronized progesterone at a dose of 200 mg per day has been reported to result in attainment of serum progesterone concentrations typically seen in the late follicular/early luteal phase of the cycle (data provided by manufacturer).

Subjects randomized to Specific Aim 3 will be treated with nasal CPAP for a period of 6 weeks. Compliance will be documented based upon results provided by a microchip sensor that detects not only if the unit is powered on, but also if the mask is being worn by the subject. These data cannot be altered by the individual and there is no access to this microsensor by the user. The subjects who have OSA will undergo one night of CPAP titration study at the end of the baseline assessment. After 6 wks of home CPAP, the experimental study outline above will be repeated with CPAP use at night. Subjects whose average nightly CPAP use is > 5 hr will be considered compliant.

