**Table D3-2. Cortisol change detectable with 80% power for varying values of  $r$ .**

$r$	Effect Size	Difference Detectable with $\sigma = 2.2$
0.25	$0.77\sigma$	1.7
0.50	$0.63\sigma$	1.4
0.75	$0.44\sigma$	1.0
0.90	$0.28\sigma$	0.6

Preliminary data in a small group of OSA+ PCOS subjects indicate that the mean cortisol level was  $10.2 \pm 2.2$  (Mean  $\pm$  SD). Using the SD from the preliminary data, for example, this study would be powered to detect a difference of  $0.63 \times 2.2 = 1.4$  if the correlation is 0.50 (see **Table 2**).

Cortisol levels at time T2 will be compared to the levels at T1 using a paired  $t$  test. Additionally, the association between the changes ( $T_2 - T_1$ ) in cortisol and in total AHI with treatment will be assessed using Pearson correlation coefficients or Spearman rank correlation coefficients, as appropriate.

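### Aim 3 asks a metabolic question but pre-specifies no metabolic test, and Table D1 conflicts with the text on two of the measurements it needs

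*Combined protocol and SAP*

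**What the plan says.** Section A (Specific Aims) states the purpose of Aim 3 as "To determine if metabolic disturbances present in PCOS women with OSA are ameliorated by the treatment of OSA with continuous positive airway pressure (CPAP". Its hypothesis, in which the levels meant are those of cortisol, has two parts: "correction of OSA in PCOS will lead to improved metabolic function which can be attributed, at least in part, to a reduction in circulating levels". The disturbances named there are raised insulin, raised glucose and abnormal lipids.

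Section D3, Statistical Considerations, Specific Aim 3, then sets the endpoint: "For this Aim the primary endpoint is the change in 24 hr cortisol concentration from baseline in response to CPAP treatment". It adds: "There are two time points of interest: baseline (T1) and end of study after receiving six weeks of CPAP (T2". Table D3-2 sizes the cortisol change only. Two analyses follow: a paired t test of cortisol at T2 against T1, and an association between the changes "in cortisol and in total AHI with treatment will be assessed using Pearson correlation coefficients", or Spearman coefficients where more suitable.

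On measurements, the methods text for Aims 2 and 3 (also numbered D3) says: "After 6 wks of home CPAP, the experimental study outline above will be repeated with CPAP use at night". The outline described in D2 contains the fsIVGTT, the 24-hour blood sampling, and the lipid and metabolomic samples. In Table D1, however, the Aim 3 column shows 1 for the fsIVGTT and 1 for the 24-hour hormonal profiles. It shows 2 for the OGTT, metabolomics, MRI/bioimpedance, adipose biopsy and adiponectin.

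**The concern.** The aim and its analysis do not meet. A significant cortisol result would show that 24-hour cortisol falls on CPAP. That would usefully confirm, in 20 women, what C8 reports in 5 (10.2 to 7.7 mcg/dL), but it would not show that metabolic function improved. The cortisol-AHI correlation ties cortisol to OSA severity, not to metabolism, so the mechanistic half of the hypothesis is not examined either.

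Many metabolic measures will be available: OGTT values, several fsIVGTT indices, lipids and a large metabolomic panel. With none singled out in advance, a metabolic claim from Aim 3 would rest on an outcome that could have been picked after the data were seen.

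The table conflict bears on the primary endpoint itself. A change in 24-hour cortisol cannot be computed from one profile, nor a change in insulin sensitivity from one fsIVGTT.

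**Working it through.** **1. The plan's own figure.** Inputs from D3, Statistical Considerations, Specific Aim 3: n = 20, two-sided alpha 0.05, power 80%, SD 2.2 mcg/dL, variance of the change 2σ²(1−r). By the normal approximation the detectable change is

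(1.960 + 0.842)/√20 × √(2(1−r)) × σ = 0.626 × √(2(1−r)) × σ.

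| r | √(2(1−r)) | in σ | × 2.2 | Table D3-2 |
|---|---|---|---|---|
| 0.25 | 1.225 | 0.767 | 1.69 | 0.77; 1.7 |
| 0.50 | 1.000 | 0.626 | 1.38 | 0.63; 1.4 |
| 0.75 | 0.707 | 0.443 | 0.97 | 0.44; 1.0 |
| 0.90 | 0.447 | 0.280 | 0.62 | 0.28; 0.6 |

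The table reproduces. It covers cortisol only.

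**2. Aim against analysis.**

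| Part of the Aim 3 hypothesis | Analysis in D3, Statistical Considerations |
|---|---|
| Metabolic function improves on CPAP | None named, tested or sized |
| Improvement is partly due to lower cortisol | None; cortisol change is related to AHI change only |
| Cortisol falls on CPAP | Paired t test, Table D3-2 |

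**3. Table against text.** The endpoint needs 24-hour cortisol at T1 and T2. The methods text repeats the outline that contains the profile and the fsIVGTT. Table D1 gives one of each for Aim 3. These are the only two rows in which the Aim 3 column differs from the Aim 2 columns. The three places cannot all be right.

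**4. What 20 women could show for a metabolic change.** With the noncentral t distribution, a paired t test at two-sided 0.05 has 80% power for 0.66 SD of the differences at n = 20, and 0.70 at n = 18 (90% of 20; D4 reports retention above 90% in similar studies).

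Illustration for 2-hour OGTT glucose. Table C4-2 gives an SEM of 5.2 in 27 women with PCOS and OSA, so SD = 5.2 × √27 = 27.0 mg/dl. The detectable change is 0.66 × √(2(1−r)) × 27.0, that is 21.9, 17.8, 12.6 and 8.0 mg/dl for r = 0.25, 0.50, 0.75 and 0.90. Two assumptions: r is not given for glucose, so the plan's own range is used; and C4 defined OSA as AHI of at least 5, whereas this study requires more than 15, so the SD may differ. The documents give no SD for insulin sensitivity in this population.

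**5. The mechanism correlation.** Using Fisher's transformation, the detectable |ρ| = tanh[(1.960 + 0.842)/√(20−3)] = tanh(0.680) = 0.59 for 80% power.

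**The case against.** A reader might infer that the metabolic question will get no answer at all. The documents do not support that. The text repeats the inpatient outline, with fsIVGTT, lipids and metabolomics, after CPAP. Table D1 lists the OGTT twice for Aim 3, and D5 calls it an outcome measure as well as a screening test. Section A and the Metabolomics part of D5 foresee comparing metabolites before and after CPAP, and Section A plans adipocyte insulin-sensitivity assays before and after treatment. D3 also reads mainly as a section for sizing primary endpoints, and D4 mentions metabolic analyses for Aim 2 that D3 does not list. All of this stands, and it limits the point to pre-specification. These statements are general, however: none names a metabolic endpoint and a test for Aim 3.

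A reader might also infer from Table D1 that the post-CPAP fsIVGTT and cortisol profile will not be collected. The table is too unreliable to show that. It lists one polysomnography in every column although Aim 2 compares AHI between time points, two of most tests for Aim 2 despite three time points, and two of most tests for Aim 1, which describes one experimental session. What stands is a conflict to be reconciled.

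Finally, one might take the fall in insulin sensitivity in C7 (7.3 to 5.5, p = 0.046, n = 6) and derive power for Aim 3. That is not safe. C7 names no test, and its p-values of 0.046 and 0.028 equal the normal-approximation Wilcoxon signed-rank values at n = 6 for rank sums of 1 and 0 (0.0464 and 0.0277). A standardised paired effect therefore cannot be recovered. Those subjects were also lean and healthy.

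**Conclusion.** The point holds as a gap in pre-specification plus an inconsistency between table and text. Both parts of the Aim 3 hypothesis, metabolic improvement and its link to cortisol, lack a pre-specified analysis. The Table D1 counts for two tests conflict with the methods text and with the definition of the primary endpoint. The cortisol test itself is sound if the outline is repeated as the text says, so this should be corrected but does not invalidate the Aim 3 primary analysis.

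The supportable scale is 0.66 SD of the differences for a metabolic change (0.70 with 18 completers), assuming roughly normal differences. The glucose figures are illustrative and rest on the borrowed SD and the assumed correlations. A cortisol-to-metabolic correlation would be reliably detected only if strong, at about 0.59 or more.

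**What to change.** 1. Reconcile the Aim 3 column of Table D1 with the methods text and with the T2−T1 endpoint, so that the primary endpoint can be computed.
2. Name one metabolic change as the single key secondary endpoint of Aim 3, for example fsIVGTT insulin sensitivity or 2-hour OGTT glucose. The choice is the investigators' and should be made before any post-CPAP data are examined. Test it T2 against T1 by paired t test, after the cortisol primary.
3. Add the correlation of cortisol change with that metabolic change beside the planned cortisol-AHI correlation, labelled exploratory because of the 0.59 figure.
4. If no metabolic endpoint is to be tested, restate Aim 3 as a question about cortisol.

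Making the metabolic change co-primary is not advised: it would need an alpha rule, and splitting alpha would cost power in a sample of 20.

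Cost: revised wording in D3, a table correction, and one or two more tests to report. No new patients are needed. No new procedures are needed either: the text already repeats the fsIVGTT, and Table D1 already lists two OGTTs for Aim 3. Because the metabolic test follows cortisol, a non-significant cortisol result would leave it descriptive.

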## D2. Screening and Specific Aim 1 Procedures

46 subjects will need to be enrolled in Specific Aim 1 in order to ensure a sample size of 20 in the group of PCOS women without OSA; this figure of 46 subjects is based on an estimated 55% prevalence of OSA among PCOS women as shown in Preliminary Studies. This calculation accounts for the effects of expected dropouts from the study. The primary outcome measures for this Aim are the differences in progesterone and estrogen concentrations between groups.

[figure not shown]
Following an initial phone screening, eligible subjects will be admitted to the GCRC in the early evening and will undergo the following screening process as described in Figure D2-1, below.

**N.B. THE SCREENING PROTOCOL DETAILED BELOW WILL PERTAIN TO ALL SPECIFIC AIMS. BASED UPON THE RESULTS OF THIS SCREENING, SUBJECTS WILL BE CLASSIFIED AS EITHER OSA NEGATIVE, IN WHICH CASE THE**

EVALUATION IS COMPLETED, OR WILL BE CLASSIFIED AS **OSA POSITIVE**. OSA POSITIVE SUBJECTS WILL THEN BE GIVEN THE OPTION TO ENTER INTO THE PROTOCOLS DETAILED IN SPECIFIC AIM 2 OR SPECIFIC AIM 3. SUBJECTS WILL BE INFORMED THAT IF THEY CHOOSE TO CONTINUE INTO AIM 2 OR AIM 3, THEY WILL BE RANDOMLY ASSIGNED USING A RANDOMIZATION SCHEDULE PREPARED BY THE GCRC BIOSTATISTICIAN, DR. [name]. SUBJECTS RANDOMLY ASSIGNED TO SPECIFIC AIM 2 WILL ALSO BE INFORMED THAT FURTHER RANDOMIZATION WILL OCCUR TO ONE OF TWO TREATMENTS, AS DETAILED BELOW.

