### D3. Statistical Considerations

#### re: Specific Aim 1

With 20 subjects per group and assuming a two-sided alpha level of 0.05, there would be approximately 80% power to detect a 0.89 SD difference in progesterone or estrogen levels between PCOS women without and PCOS women with OSA. These values are derived from data obtained in a group of 10 PCOS women without OSA. Using the SD from the preliminary data, this study would be powered to detect a 42% difference in hormone levels between groups.

46 subjects will need to be enrolled for this Aim in order to ensure a sample size of 20 in the group of PCOS women without OSA; this figure of 46 subjects is based on an estimated 55% prevalence of OSA among PCOS women as shown in Preliminary Studies.

Progesterone and estrogen levels will be compared between the two groups using a two sample *t* test. A log transformation of the data will be performed if there is evidence of non-normality. Statistical correction will be made for multiple comparisons between groups.

#### re: Specific Aims 2 and 3

The PCOS women with OSA studied in Aim 1 plus additionally enrolled PCOS women with OSA (for a total of 60 subjects) will be randomized in a ratio of 2:1 to participate in Aim 2 (n=40) or Aim 3 (n=20). Block randomization will be performed using computer-generated random numbers.

#### • Specific Aim 2

For this Aim, there are three time points of interest: baseline (T1), six weeks after administration of depot leuprolide (T2), and at the end of study after receiving six weeks of either estrogen or progesterone

(T3). Treatment assignment to either estrogen (n=20) or progesterone (n=20) will be randomized using computer-generated random numbers.

If the variance in AHI is denoted by  $\sigma^2$  and the correlation between pre- and post-treatment AHI by  $r$ , then the variance of the change in AHI is given by  $2\sigma^2(1-r)$ . With 20 subjects per group and assuming a two-sided alpha level of 0.05, the **Table D3-1** below lists the difference in AHI change detectable between the two treatment groups with 80% power for varying values of  $r$ .

**Table D3-1. Difference in AHI change detectable between the two treatment groups with 80% power for varying values of  $r$ .**

$r$	Effect Size	Difference Detectable with $\sigma = 8$
0.25	$1.08\sigma$	8.6
0.50	$0.89\sigma$	7.1
0.75	$0.63\sigma$	5.0
0.90	$0.40\sigma$	3.2

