**D4. Potential pitfalls and plans for their resolution**

re: Specific Aim 1. In studies conducted under Specific Aim 1, subjects will be recruited to participate in a wide variety of procedures over a number of weeks. Recruitment and retention may pose challenges, however we have longstanding experience with studies of this nature and our recruitment procedures have been successful to date; our retention rates in similar studies has been over 90%. Subjects are contacted on a regular basis by our study coordinator. Subjects also receive monetary compensation for participation in the protocols. We have successfully recruited subjects in the past through cooperation with other physicians who care for patients with PCOS and we plan to do so again in the event that recruitment goals are lagging.

re: Specific Aim 2. Studies in this Aim are anticipated to flow smoothly. Potential problems include drop-outs related to intolerance/untoward effects of study medication and lack of compliance. It is anticipated that additional subjects may need to be recruited to replace the drop-outs. Another potential pitfall is that the degree of testosterone suppression expected after depot-leuprolide administration may be insufficient (i.e., testosterone levels may remain above the normal female range). If this proves to be the case, we will use testosterone concentration as a covariate in our analyses related to metabolic changes pre- and post-leuprolide. Likewise, even though micronized estrogen and progesterone are optimized for oral absorption, if serum levels of estrogen and progesterone achieved are below the expected range observed in normal women, we will use these hormone concentrations as covariates in our statistical analyses. Although transdermal (patch or cream preparations) were an alternative to oral hormone therapy, the assessment of compliance with their use would have posed challenges. Pill counts, patient contact on a regular basis, and measurement of hormone levels in blood will be used to ensure and document use of study medication.

re: Specific Aim 3. This protocol requires high levels of commitment from study subjects who must use CPAP on a regular basis for the duration of the study. Compliance with CPAP use is automatically recorded and powering on the device can be differentiated from patient use via sensors incorporated into the CPAP mask. Thus, we will have device-generated compliance records.

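### Table D3-2 states 80% power for Aim 3, but with the planned paired t test and 20 women the power at its printed changes is 75% to 76%

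*Combined protocol and SAP*

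**What the plan says.** The Aim 3 part of section D3, Statistical Considerations, makes the change in 24-hour cortisol the primary endpoint and sets out the sizing as follows.

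- Sample and test level: "With 20 subjects and assuming a two-sided alpha level of 0.05".
- Variance: with SD σ and pre/post correlation r, "then the variance of the change in cortisol is given by" 2σ²(1−r).
- Result: Table D3-2 "lists the cortisol change detectable with 80% power for varying values of" r. The effect sizes are 0.77, 0.63, 0.44 and 0.28 σ for r = 0.25, 0.50, 0.75 and 0.90. With σ = 2.2 they are printed as 1.7, 1.4, 1.0 and 0.6.
- Analysis: a paired t test of T2 against T1.

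The Aim 2 part of the same section has the same structure. It starts from "With 20 subjects per group and assuming a two-sided alpha level of 0.05", and Table D3-1 "lists the difference in AHI change detectable between the two treatment groups with 80% power": 1.08, 0.89, 0.63 and 0.40 σ, or 8.6, 7.1, 5.0 and 3.2 events per hour with σ = 8. The planned test is a two-sample t test on the change from T1 to T3.

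On drop-out, 60 women are randomised, 40 to Aim 2 and 20 to Aim 3. These are the same numbers that enter the power tables. Section D2 says of the 46 women in Aim 1: "This calculation accounts for the effects of expected dropouts from the study". Section D4 expects that drop-outs may have to be replaced, but says so only in its Aim 2 paragraph. Its Aim 3 paragraph covers compliance recording by the CPAP device and nothing on loss of subjects. The Aim 1 paragraph of D4 reports past experience: "our retention rates in similar studies has been over 90" percent.

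**The concern.** A detectable difference at a stated power depends on the test that will be used. A paired t test on 20 women has to estimate the SD of the change from the same 20 women. Its critical value is 2.093 (19 degrees of freedom), compared with 1.960 for a test with known variance. A table built on 1.960 therefore credits the design with power that the planned test does not have. Aim 3 is a single group of 20, so the effect is larger there than in Aim 2, which has 38 degrees of freedom.

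What is at stake is the accuracy of the sizing statement for the Aim 3 primary endpoint. If it is too optimistic, a non-significant cortisol result would be read as stronger evidence against a change of the tabulated size than it is.

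**Working it through.** **Inputs.** Two-sided alpha 0.05, stated power 80%, n = 20 (Aim 3) and 20 per group (Aim 2), variance of change 2σ²(1−r), σ = 2.2 for cortisol and 8 for AHI, paired and two-sample t tests. All are from section D3, Statistical Considerations.

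**Step 1: reproduce the plan's figures.** With normal quantiles, 1.960 + 0.842 = 2.802.

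- Aim 3: 2.802 × √(2(1−r)) / √20 = 0.767, 0.626, 0.443, 0.280 σ. The table prints 0.77, 0.63, 0.44, 0.28.
- Aim 2: 2.802 × √(2(1−r)) × √(2/20) = 1.085, 0.886, 0.626, 0.396 σ. The table prints 1.08, 0.89, 0.63, 0.40.

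Both tables are recovered to rounding. The alternatives that were tried do not match: noncentral t gives 0.809, 0.660, 0.467, 0.295 σ for Aim 3, and a one-sided normal calculation gives 0.681, 0.556, 0.393, 0.249 σ.

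**Step 2: Aim 3 power with the planned test.** For a printed effect e (in σ), the standardised change is d = e / √(2(1−r)) and the noncentrality is d√n. Power is the probability that a noncentral t variable with n−1 degrees of freedom exceeds the critical value. For r = 0.50, √(2(1−r)) = 1, d = 0.63, the noncentrality is 0.63 × √20 = 2.817, and power is 76.2%.

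| r | Printed effect (σ) | Power, n = 20 | Effect for 80% power, n = 20 (σ) | × 2.2 | Printed |
|---|---|---|---|---|---|
| 0.25 | 0.77 | 76.0% | 0.809 | 1.78 | 1.7 |
| 0.50 | 0.63 | 76.2% | 0.660 | 1.45 | 1.4 |
| 0.75 | 0.44 | 75.2% | 0.467 | 1.03 | 1.0 |
| 0.90 | 0.28 | 75.7% | 0.295 | 0.65 | 0.6 |

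The chance of missing the printed effects is 100 − 76.2 = 23.8% to 100 − 75.2 = 24.8%. At the unrounded effect, power is 75.7% in every row, because r cancels. It reaches 80.0% at 22 complete pairs.

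**Step 3: Aim 3 with fewer completers (assumption).** The plan gives no loss rate for Aim 3. If one or two of the 20 women lack a T2 profile and are not replaced, power at the printed effects is:

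| Completers | r = 0.25 | r = 0.50 | r = 0.75 | r = 0.90 |
|---|---|---|---|---|
| 19 | 73.6% | 73.8% | 72.8% | 73.3% |
| 18 | 71.0% | 71.2% | 70.2% | 70.7% |

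Eighteen is 20 × 0.90, the lower edge of the past retention reported in D4.

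**Step 4: Aim 2 with the planned test.** With 38 degrees of freedom and noncentrality d√(20/2), power at the printed effects is 77.6%, 78.3%, 78.4% and 78.7%. The differences detectable with 80% power are 1.114, 0.909, 0.643 and 0.407 σ. Multiplied by 8, they are 8.9, 7.3, 5.1 and 3.3, against the printed 8.6, 7.1, 5.0 and 3.2.

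**The case against.** The best case for leaving the tables alone is that the error hardly matters. They are grids over an unknown r. Within Table D3-2 the detectable change runs from 0.28 to 0.77 σ, almost threefold, while the t correction moves each row by about 5%. The preliminary data in section C8 show a fall in mean 24-hour cortisol of 10.2 − 7.7 = 2.5, beyond every row. With SD 2.2, paired t power for 2.5 is 99.5% at r = 0.50 and 96.0% at r = 0.25, even with 18 women. This stands as a judgement of practical weight. It does not make 80% the right power at the printed changes. The preliminary series also had only 5 women and 8 weeks of CPAP, where the trial has 6.

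Two stronger readings are tempting, and the documents do not support them.

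- A reader might infer that Aim 3 as designed has about 71% power because the plan expects 90% retention. The retention figure is over 90%, describes similar past studies and stands in the Aim 1 paragraph. It is neither a planning rate nor a figure for CPAP. With the 20 women of the design, the miss rate is 24% to 25%. Anything higher rests on an assumed loss.
- A reader might infer that Aim 2 fails in the same way. At 20 per group it loses 1.3 to 2.4 points, and D4 anticipates replacing drop-outs there, so a calculation with unreplaced losses does not describe that plan.

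Aim 1 is also a weak standard of comparison. Its 46 women yield 46 × 0.45 = 20.7 without OSA, which leaves almost no margin over 20 despite the statement on drop-outs. Its 0.89 SD has t power of 78.3%, although the plan there claims only approximate 80% power.

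**Conclusion.** Wrong as written, and minor. The 80% attached to Table D3-2 belongs to a normal-quantile calculation; for the planned paired t test with 20 complete pairs it is 75% to 76%. This needs no assumption beyond the plan's own n, alpha, variance formula and printed effect sizes, together with the usual normality of the changes. If the rounded cortisol values are used in place of the σ values, rounding spreads the result to between 73.5% and 77.9%, all still below 80%.

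The absence of a stated drop-out allowance or replacement rule for Aim 3 is a real gap, but its size is conditional on the losses assumed. The Aim 2 table deserves the same correction for consistency; its shortfall is marginal.

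**What to change.** Restate Table D3-2 from the noncentral t distribution at n = 20, using the 80%-power effects and cortisol values in the Aim 3 table above, and change the worked example at r = 0.50 from 1.4 to 1.45. Alternatively, keep the printed changes and give their power as about 76%.

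Add one sentence saying whether Aim 3 drop-outs will be replaced, and one sensitivity line, labelled as an assumption, with the power for 19 and 18 completers. As a companion correction, restate Table D3-1 with 8.9, 7.3, 5.1 and 3.3 events per hour.

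The cost is slightly less favourable figures. Restating them requires no additional patients and leaves the planned analyses unchanged.
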